10.4.3 Safety Analysis

Safety will be assessed through the analysis of the reported incidence of treatment-emergent AEs. Treatment-emergent AEs are those with an onset on or after the initiation of therapy, and will be graded according to NCI CTCAE Version 5. A copy of CTCAE scoring system may be downloaded from: http://evs.nci.nih.gov/ftp1/CTCAE/CTCAE_5.0_2010-06-14_QuickReference_8.5x11.pdf.

The AEs will be coded using Medical Dictionary for Regulatory Activities (MedDRA) and summarized using system organ class and preferred term for all patients in the Safety Analysis Set. In addition, summaries of SAEs, AEs leading to treatment discontinuation, AEs by maximum NCI CTCAE grade, and AEs related to study treatment will also be presented.

Other safety endpoints including laboratory results, vital signs, ECG findings, and other protocol-specified tests will be listed and/or summarized for all patients in the Safety Analysis Set.

Concomitant medications will be coded using the World Health Organization-Drug Dictionary and they will be listed and summarized.

10.5 Analysis Time Points

10.5.1 Final Analysis

The final analysis of the study will occur following the last visit of the last patient.

CONFIDENTIAL

STUDY DRUG: INCB039110 (ITACITINIB)
FINAL PROTOCOL DATE: 26 OCTOBER 2021

INNOVATIONS STUDY NUMBER: BMT 29
VERSION 4

10.5.2 Safety Review

The clinical trial will be placed on hold if itacitinib is discontinued due to AEs in greater than 5/10, 10/20, or 15/30 patients.

10.5.3 Efficacy Analysis

The primary efficacy analysis will be done on consolidated data following 6 months of treatment (between the end of Cycle 6 and the beginning of Cycle 7).

11. SAFETY REPORTING AND ANALYSES

Safety assessments will consist of monitoring and recording protocol-defined AEs and serious AEs (SAEs), measurement of protocol-specified hematology, clinical chemistry, and urinalysis variables, and measurement of protocol-specified vital signs and other protocol-specified tests that are deemed critical to the safety evaluation of the study drug.

The Principal Investigator is responsible for recognizing and reporting AEs to the SC Innovations Safety Department (see Section 11.1.5). It is Innovations' responsibility to report relevant SAEs to the applicable local, national, or international regulatory bodies. In addition, Investigators must report SAEs and follow-up information to their responsible IRB according to the policies of each IRB.

The Principal Investigator is also responsible for ensuring that every staff member involved in the study is familiar with the content of this section.

11.1 Definitions

11.1.1 Adverse Events

Adverse event means any untoward medical occurrence associated with the use of a drug in humans, whether or not considered drug-related. An AE (also known as adverse experience) can be any unfavorable and unintended sign (e.g., an abnormal laboratory finding), symptom, or disease temporarily associated with the use of a drug, without any judgment about causality. An AE can arise with any use of the drug (e.g., off-label use, use in combination with another drug) and with any route of administration, formulation, or dose (including overdose).

11.1.2 Serious Adverse Events

An AE or a suspected adverse reaction (SAR) is considered “serious” if it results in any of the following outcomes:

- Death**
- A life-threatening AE**
- Inpatient hospitalization or prolongation of an existing hospitalization**
- A persistent or significant incapacity or substantial disruption of the ability to conduct normal life functions**
- A congenital anomaly/birth defect**

CONFIDENTIAL

STUDY DRUG: INCB039110 (ITACITINIB)
FINAL PROTOCOL DATE: 26 OCTOBER 2021

INNOVATIONS STUDY NUMBER: BMT 29
VERSION 4

Important medical events that may not result in death, be life-threatening, or require hospitalization may be considered serious when, based upon appropriate medical judgment, they may jeopardize the patient and may require medical or surgical intervention to prevent one of the outcomes listed in this definition. Examples of such medical events include allergic bronchospasm requiring intensive treatment in an emergency room or at home, blood dyscrasias or convulsions that do not result in hospitalization, or development of drug dependency or drug abuse.

It is important to distinguish between “serious” and “severe” when describing AEs, as the terms are not synonymous. Severity is a measure of intensity; however, an AE of severe intensity need not necessarily be considered serious. Seriousness serves as the guide for defining regulatory reporting obligations. “Serious” is a regulatory definition and is based on patient/event outcome or action usually associated with events that pose a threat to a patient’s life or vital functions. For example, nausea which persists for several hours may be considered severe nausea, but may not be considered an SAE. On the other hand, a stroke which results in only a limited degree of disability may be considered only a mild stroke, but would be considered an SAE. Severity and seriousness should be independently assessed when recording AEs on the eCRF and SAEs on the SAE Report Form.

11.1.3 Adverse Reaction

An adverse reaction means any AE caused by a drug. Adverse reactions are a subset of all suspected adverse reactions where there is a reason to conclude that the drug caused the event.

11.1.4 Suspected Adverse Reaction

Suspected adverse reaction means any AE for which there is a reasonable possibility that the drug caused the AE. Reasonable possibility means that there is evidence to suggest a causal relationship between the drug and the AE. A suspected adverse reaction implies a lesser degree of certainty about causality than adverse reaction, which means any AE caused by a drug.

11.1.5 Recording and Reporting of Adverse Events

11.1.5.1 Recording of Adverse Events

All AEs will be recorded in the eCRF for all patients during the course of the research study, and the Investigator will give his or her opinion as to the relationship of the AE to the study treatment (i.e., whether the event is related or unrelated to study drug administration).

A description of the event, including its date of onset and resolution, whether it constitutes a SAE or not, any action taken (e.g., changes to study treatment), and outcome, should be provided, along with the Investigator’s assessment of causality (i.e., the relationship to the study treatment). For an AE to be a suspected treatment-related event there should be at least a reasonable possibility of a causal relationship between the protocol treatment and the AE. Adverse events will be graded according to the NCI CTCAE Version 5, and changes will be documented.

If the AE is serious, it should be reported immediately to the Innovations Safety Department. Other untoward events occurring in the framework of a clinical study are to be recorded as AEs (i.e., AEs that occur prior to assignment of study treatment that are related to a protocol-

CONFIDENTIAL

STUDY DRUG: INCB039110 (ITACITINIB)
FINAL PROTOCOL DATE: 26 OCTOBER 2021

INNOVATIONS STUDY NUMBER: BMT 29
VERSION 4

mandated intervention, including invasive procedures such as biopsies, medication washout, or no treatment run-in).

Any clinically significant signs and symptoms; abnormal test findings; changes in physical examination; hypersensitivity; and other measurements that occur will be reported as an AE, and collected on the relevant eCRF screen.

Test findings will be reported as an AE if the test result requires an adjustment in the study drug(s) or discontinuation of treatment; and/ or test findings require additional testing or surgical intervention; a test result or finding is associated with accompanying symptoms; or a test result is considered to be an AE by the Investigator.

11.1.5.2 Reporting Period for Adverse Events

All AEs regardless of seriousness or relationship to the study treatment spanning from the signing of the informed consent form until 30 calendar days after discontinuation or completion of study treatment, as defined by this clinical study protocol, are to be recorded on the corresponding screen(s) included in the eCRF.

All AEs resulting in discontinuation from the study should be followed until resolution or stabilization. All new AEs occurring during this period must be reported and followed until resolution unless, in the opinion of the Investigator, the AE or laboratory abnormality/ies are not likely to improve because of the underlying disease. In this case, the Investigator must record his or her reasoning for this decision in the patient's medical record.

After 30 days of completion of protocol-specific treatment or discontinuation, only AEs, SAEs, or deaths assessed by the Investigator as treatment-related are to be reported.

11.1.6 Assessment of Adverse Events

All AEs and SAEs whether volunteered by the patient, discovered by study personnel during questioning, or detected through physical examination, laboratory test, or other means will be reported appropriately. Each reported AE or SAE will be described by its duration (i.e., start and end dates), regulatory seriousness criteria if applicable, suspected relationship to the study drug (see following guidance), and actions taken.

To ensure consistency of AE and SAE causality assessments, Investigators should apply the following general guideline:

YES: There is a plausible temporal relationship between the onset of the AE and administration of the study medication, and the AE cannot be readily explained by the patient's clinical state, intercurrent illness, or concomitant therapies, and/or the AE follows a known pattern of response to the study drug, and/or the AE abates or resolves upon discontinuation of the study drug or dose reduction and, if applicable, reappears upon re-challenge.

NO: Evidence exists that the AE has an etiology other than the study drug (e.g., pre-existing medical condition, underlying disease, intercurrent illness, or concomitant medication), and/or the AE has no plausible temporal relationship to study drug administration (e.g., cancer diagnosed 2 days after first dose of study drug).

CONFIDENTIAL

STUDY DRUG: INCB039110 (ITACITINIB)
FINAL PROTOCOL DATE: 26 OCTOBER 2021

INNOVATIONS STUDY NUMBER: BMT 29
VERSION 4

11.2 Serious Adverse Event Reporting by Investigators

Adverse events classified by the treating Investigator as serious require expeditious handling and reporting to the Innovations Safety Department in order to comply with regulatory requirements. Determination of life-threatening or serious is based on the opinion of the Investigator.

Serious AEs may occur at any time from the signing of the informed consent form through the 30-day follow-up period after the last dose of study drug. **The Innovations Safety Department must be notified of all SAEs, regardless of causality, within 24 hours of the first knowledge of the event by the treating physician or research personnel.**

To report an SAE, the SAE Report Form should be completed with the necessary information.

The SAE report should be sent to the Innovations Safety Department via fax or e-mail using the following contact information (during both business and non-business hours):

Sarah Cannon Innovations Safety Department

Safety Dept. [contact]

Safety Dept. Email: [contact]

Transmission of the SAE report should be confirmed by the site personnel submitting the report.

Follow-up information for SAEs and information on non-serious AEs that become serious should also be reported to the Innovations Safety Department as soon as it is available; these reports should be submitted using the Innovations SAE Report Form.

Investigators must report SAEs and follow-up information to their responsible IRB according to the policies of the responsible IRB.

11.3 Recording of Adverse Events and Serious Adverse Events

11.3.1 Diagnosis versus Signs and Symptoms

All AEs should be recorded individually in the patient's own words (verbatim) unless, in the opinion of the Principal Investigator or designated physician, the AEs constitute components of a recognized condition, disease, or syndrome. In the latter case, the condition, disease, or syndrome should be named rather than each individual sign or symptom. If a constellation of signs and/or symptoms cannot be medically characterized as a single diagnosis or syndrome at the time of reporting, each individual event should be recorded as an AE or SAE as appropriate on the relevant form(s) (SAE Report Form and/or AE eCRF screen). If a diagnosis is subsequently established, it should be reported as follow-up information is available. If a diagnosis is determined subsequent to the reporting of the constellation of symptoms, the signs/symptoms should be updated to reflect the diagnosis.

Progression of malignancy (including fatal outcomes), if documented by use of appropriate method (for example, as per RECIST criteria for solid tumors), should not be reported as an SAE.

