1. INTRODUCTION

1.1 Background and Study Rationale

During the last 2 decades, the number of patients undergoing allogeneic hematopoietic stem cell transplantation (allo-HSCT) has more than doubled worldwide. Graft-versus-host disease (GVHD) remains the major hurdle to improve allo-HSCT outcome. High mortality rates are seen for patients suffering from steroid-refractory (SR) acute GVHD (aGVHD), while chronic GVHD (cGVHD) is associated with a decreased quality of life (Zeiser et al. 2015).

Depending on a number of patient- and transplant-related variables, the incidence of aGVHD ranges from 10% to 80% with symptoms usually developing 2 to 3 weeks post-transplant. It is estimated that cGVHD affects 30% to 70% of allo-HSCT recipients surviving beyond 100 days, with a median onset of 4 to 6 months following HSCT. Although cGVHD is associated with reduced relapse rates in patients transplanted for leukemia, cGVHD remains the leading cause of late death in HSCT survivors (Garnett et al. 2013).

Management of GVHD is challenging. Immunosuppression with corticosteroids forms the basis of first-line therapy in both aGVHD and cGVHD, but sustained responses are usually seen in <50% of patients and there remains no standard 2nd- and 3rd-line treatment for SR-cGVHD. While evaluation of further therapeutic options is complicated, alternative systematic therapy strategies and the identification of novel therapeutic targets are needed to improve outcomes.

A retrospective survey of 95 patients treated for SR-aGVHD and SR-cGVHD with a Janus kinase (JAK) 1/2 inhibitor, ruxolitinib, in 19 European and US transplant centers highlighted the therapeutic potential of JAK-inhibitors in the treatment of SR-GVHD. Treatment with ruxolitinib was considered safe and well tolerated in the heavily pre-treated patient population. An overall response rate (ORR) above 80% was reported for both SR-aGVHD and SR-cGVHD with median time to response being rapid (<2 weeks). Additional follow-up for patients with SR-aGVHD and SR-cGVHD reported 1-year ORRs of 62.4% and 92.7%, respectively (Zeiser et al. 2015).

A novel, potent, and selective inhibitor of the JAK family of protein tyrosine kinases (TYKs) with selectivity for JAK1, itacitinib (INCB039110 adipate), is the investigational product in this study. Itacitinib is being developed by Incyte Corporation for the treatment of GVHD, solid tumors, B-cell malignancies, myeloproliferative neoplasms, and inflammatory diseases.

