2.2 Secondary Objectives

The secondary objectives of this study are to determine the:

- Ability to either withdraw or decrease steroids to <0.5 mg/kg of methylprednisolone or equivalent
- Overall survival
- Safety and tolerability of itacitinib in patients with SR-cGVHD
- Quality of life impact using the Lee Symptom Scale from screening until the end-of-treatment (EOT) visit
- Recurrence or progression of cGVHD and
- Relapse rate of underlying malignancy.

CONFIDENTIAL

STUDY DRUG: INCB039110 (ITACITINIB)
FINAL PROTOCOL DATE: 26 OCTOBER 2021

INNOVATIONS STUDY NUMBER: BMT 29
VERSION 4

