3.2 Exclusion Criteria

Patients who meet any of the following criteria will be excluded from study entry:

1. Receiving concomitant JAK inhibitor for cGVHD; prior treatment with a JAK inhibitor for aGVHD is permitted if treatment was stopped more than 60 days prior to study start. Patients are eligible if JAK inhibitors for treatment of cGVHD are stopped due to side effects and not due to refractoriness.
2. Treatment with any other investigational agent, device, or procedure, within 28 days (or 5 half-lives, whichever is longer) of enrollment. For previous study drugs where 5 half-lives is ≤ 28 days, a minimum of 10 days between termination of that study drug and administration of itacitinib is required.
3. Presence of current secondary malignancies with the exception of previously treated *in situ* carcinoma (i.e., noninvasive), cervical carcinoma Stage 1B or less, and noninvasive basal cell or squamous cell skin carcinoma.
4. Pregnant or nursing (lactating) women
5. Patients with relapsed primary malignancy, or who have been treated for relapse after the allo-HSCT was performed
6. History of progressive multifocal leukoencephalopathy
7. Evidence of the following infections:
 - Active uncontrolled bacterial, fungal, parasitic, or viral infection. Infections are considered controlled if appropriate therapy has been instituted and, at the time of screening, no signs of infection progression are present. Progression of infection

CONFIDENTIAL

STUDY DRUG: INCB039110 (ITACITINIB)
FINAL PROTOCOL DATE: 26 OCTOBER 2021

INNOVATIONS STUDY NUMBER: BMT 29
VERSION 4

is defined as hemodynamic instability attributable to sepsis, new symptoms, worsening physical signs or radiographic findings attributable to infection. Persisting fever without other signs or symptoms will not be interpreted as progressing infection.

- Known human immunodeficiency virus (HIV) infection
- Active tuberculosis infection that developed after allo-HSCT
- Active viral infection confirmed by polymerase chain reaction (PCR) for the BK virus (a polyoma virus), cytomegalovirus (CMV), Epstein-Barr virus (EBV), and human herpes virus 6 (HHV-6).
- Active hepatitis B virus (HBV) or hepatitis C virus (HCV) infection that requires treatment, or at risk for HBV reactivation (i.e., positive HBsAg).

8. Severe organ dysfunction unrelated to underlying GVHD, including:

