8.3 Tapering of Itacitinib

If a patient has achieved CR or PR after 6 months of treatment, Investigators may begin to taper the dose of itacitinib by 1 dose level provided corticosteroids have been discontinued for at least 8 weeks following institutional guidelines. Subjects must not be experiencing any Grade 2 or higher hematologic toxicity related to study treatment or symptoms of an active infection.

Investigators wishing to initiate a taper of itacitinib at an earlier time point may do so upon consultation with and approval from the Study Chair.

If GVHD signs/symptoms worsen during the taper of itacitinib, the dose may be escalated by 1 dose level. If the patient requires additional systemic therapy (includes restarting of corticosteroids), then the patient would be considered as having disease progression (PD) and would be withdrawn from study treatment.

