11.3.4 Deaths

Deaths that occur during the protocol-specified AE reporting period that are attributed solely to progression of disease, as determined by the Investigator, will be recorded on the “End of Study” eCRF screen. All other on-study deaths, regardless of attribution, will be recorded on an SAE Report Form and expeditiously reported to the Innovations Safety Department.

When recording a SAE with an outcome of death, the event or condition that caused or contributed to the fatal outcome should be recorded as the single medical concept on the SAE Report Form and Adverse Event eCRF screen. If the cause of death is unknown and cannot be ascertained at the time of reporting, record “Death NOS” (death, cause unknown) on the eCRF Adverse Event screen. During post-study survival follow-up, deaths attributed to progression of disease will be recorded only on the “Follow-Up Summary” and “Death Page” eCRF screens.

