11.3.6 Pre-Existing Medical Conditions

A pre-existing medical condition is one that is present at the start of the study. Such conditions should be recorded on the General Medical History eCRF screen. A pre-existing medical condition should be recorded as an AE or SAE only if the frequency, severity, or character of the condition worsens during the study. When recording such events on an SAE Report Form and/or AE eCRF screen, it is important to convey the concept that the pre-existing condition has changed by including applicable descriptors.

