11.3.7 New Cancers

The development of a new primary cancer should be regarded as an AE and will generally meet at least one of the seriousness criteria (see Section 11.1.2). New primary cancers are those that are not the primary reason for the administration of the study treatment and have developed after the inclusion of the patient into the study. They do not include metastases of the original cancer. Symptoms of metastasis or the metastasis itself should not be reported as an AE/SAE, as they are considered to be disease progression.

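### Section 11.3.1 exempts documented malignancy progression from SAE reporting; in this cGVHD trial that takes new relapse out of expedited reporting and the SAE summary, though not out of the database

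*Combined protocol and SAP*

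**What the plan says.** All references are to the combined protocol and SAP.

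- **Exemption.** Section 11.3.1: "Progression of malignancy (including fatal outcomes), if documented by use of appropriate method" should not go forward as an SAE. Its example of an appropriate method is RECIST for solid tumors.
- **Metastasis.** Section 11.3.7: "Symptoms of metastasis or the metastasis itself should not be reported as an AE/SAE, as they are considered to be disease progression".
- **Deaths.** Section 11.3.4: "Deaths that occur during the protocol-specified AE reporting period that are attributed solely to progression of disease" go on the End of Study screen of the eCRF. All other on-study deaths go on an SAE form. Which disease is meant is not stated.
- **Second use of the term.** Section 8.3 uses disease progression (PD) for cGVHD that needs more systemic therapy during the itacitinib taper.
- **Entry.** Section 3.2 excludes "Patients with relapsed primary malignancy, or who have been treated for relapse after the allo-HSCT was performed".
- **Relapse as an outcome.** Section 2.2 lists "Relapse rate of underlying malignancy" as a secondary objective. Section 6.3.1 and Appendix D (footnote j) have it assessed on Day 1 of each cycle, at end of treatment and in follow-up, with the date on the eCRF.
- **Pre-existing conditions.** Section 11.3.6: such a condition "should be recorded as an AE or SAE only if the frequency, severity, or character of the condition worsens during the study". cGVHD is neither named nor exempted.
- **What SAE status triggers.** Notice to the sponsor's safety department within 24 hours (11.2), forwarding to the drug supplier's pharmacovigilance within 1 business day (11.4), and inclusion in the SAE summary (10.4.3).

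**The concern.** An exemption for progression normally keeps the expected course of the treated disease out of expedited reporting, because that course is the efficacy endpoint. Here the treated disease is cGVHD, and the exemption falls on a different condition.

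That condition is one the drug could plausibly make worse. Section 1.1 begins a sentence with "Although cGVHD is associated with reduced relapse rates in patients transplanted for leukemia", so suppressing cGVHD might weaken that protection. Section 1.2 answers with murine evidence that the graft-versus-tumor effect is preserved, and Section 1.1.2 says this is the first study of the drug in steroid-refractory cGVHD. A cluster of relapses, some fatal, is therefore a signal one would want to reach the safety department and the drug supplier promptly.

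A second, smaller issue runs the other way. No rule says whether worsening cGVHD is an AE. If some investigators code it as one under 11.3.6 and others do not, the table of AEs leading to discontinuation and the hold rule in 10.5.2 depend in part on coding habit.

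**Working it through.** The plan gives no figure on this point. Its one design figure, a confidence interval width of 0.266 at 20% of 40 patients, reproduces (exact limits for 8/40: 0.0905 to 0.3565, width 0.2660) but plays no part here.

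**1. What the exemption covers.** Relapsed patients cannot enter (3.2), so no enrolled patient should have an existing relapse to progress. Malignancy progression on study is then a new relapse. Sections 6.4 and 6.5 use progression of the underlying malignancy for the event that Section 3.3 calls relapse.

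**2. What is lost and what is kept.**

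| Route | Documented relapse under 11.3.1 |
|---|---|
| 24-hour notice (11.2) | bypassed |
| Forwarding to the supplier (11.4) | bypassed |
| SAE summary (10.4.3) | absent |
| AE recording (11.1.5) | not barred |
| Relapse date on the eCRF (Appendix D, footnote j) | collected |

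**3. How many patients.** Expected number = 40 × rate, with the rate assumed and taken to apply within the SAE reporting period.

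- 5%: 40 × 0.05 = 2; chance of at least one = 1 − 0.95^40 = 87%.
- 15%: 40 × 0.15 = 6; chance of at least one = 1 − 0.85^40 = 99.8%.

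**4. The hold rule and cGVHD stops.** Section 10.5.2 holds the trial when more than 5/10, 10/20 or 15/30 patients discontinue due to AEs, that is at 6, 11 or 16. With p the probability that a patient counts as an AE discontinuation, P(hold) is the sum over the three looks of the probability of first crossing. Each block of ten adds a Binomial(10, p) count, and paths that have crossed are removed.

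Assumptions, none from the documents: toxicity stops in 15%, cGVHD stops in 20% to 40%, no overlap between them, all counted by each look, and a fraction f of cGVHD stops coded as AE discontinuations. Then p = 0.15 + f × (0.20 to 0.40).

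| f | p | P(hold) |
|---|---|---|
| 0 | 0.15 | 0.1% |
| 1/4 | 0.20 to 0.25 | 0.7% to 2.2% |
| 1 | 0.35 to 0.55 | 12% to 76% |

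The result depends mainly on f, which is unknown.

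**The case against.** The strongest reply is that relapse is well captured. It is a secondary objective and a listed reason to stop treatment (3.3), is assessed every cycle, and is dated on an eCRF that Section 14.4 wants kept current so the sponsor can review patients throughout. Using endpoint pages instead of SAE forms is a recognised choice. Section 11.3.1 bars SAE reporting only, not AE recording, and only for progression documented by a suitable method, while Appendix D requires no formal re-staging.

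Most of this stands. A reader might infer that the safety data miss relapse altogether, or that it would first be seen at the final analysis. The documents support neither. What the reply does not restore is expedited handling: a current eCRF is not a 24-hour notice, and neither the forwarding rule nor the SAE summary draws on the relapse page.

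On cGVHD, the reply is that the protocol separates its progression from toxicity: as distinct stopping reasons in 3.3, as distinct events in 6.4 and 6.5, and as treatment failure in 5.2.3 and 7.2. That is fair. A reader might infer from 11.3.6 that worsening cGVHD is an AE by rule, but that section is generic and the inference is not stated anywhere. What remains is an ambiguity, because no section says how such a stop counts in 10.4.3 or 10.5.2.

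**Conclusion.** The concern holds for expedited reporting. Followed as written, Section 11.3.1 keeps documented relapse, fatal cases included, out of 24-hour notification, forwarding to the drug supplier and the SAE summary. At an assumed 5% to 15% this touches 2 to 6 of 40 patients. The number of SAE reports forgone may be smaller, since a relapse must also meet a seriousness criterion. That relapse is a harm of treatment is a plausible reading of Sections 1.1 and 1.2; the protocol does not list it as a known risk.

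The cGVHD point is a secondary clarification. A reader might take the 12% to 76% chance of a hold as its size, but that requires every cGVHD stop to be coded as an AE discontinuation. If a quarter are, the chance is 0.7% to 2.2%; if none are, 0.1%. The documents do not say which applies.

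**What to change.** 1. **Section 11.3.1.** Replace the sentence, including its RECIST example, with: *Relapse or progression of the underlying malignancy that meets a seriousness criterion in Section 11.1.2, including any fatal case, is reported as an SAE within 24 hours.*
2. **Sections 11.3.4 and 11.3.7.** Bring both into line. Otherwise a fatal relapse would be reportable under 11.3.1 yet still sent to the End of Study screen by 11.3.4, and the metastasis sentence would keep its own exemption.
3. **Definition.** Define disease progression once, separating malignancy from cGVHD, and use it consistently in 8.3, 11.3.1, 11.3.4 and 11.3.7. State which condition the death rule in 11.3.4 covers.
4. **Counting rule.** Add to 10.4.3 and 10.5.2 that a stop for cGVHD progression or lack of response, already a separate reason in 3.3, does not count as an AE discontinuation unless the event is judged related to itacitinib. Cross-refer from 11.3.6.

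The cost is a few sentences, a note to sites and a few more SAE reports. Treatment, visits and sample size are unchanged.
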